#### 8.1.2 Serious Adverse Event

An SAE is defined as, but not limited to, any untoward medical occurrence that:

- Results in death.
- Is life-threatening.
- Requires inpatient hospitalization or prolongation of existing hospitalization.
- Results in persistent or significant disability/incapacity, or,
- Is a congenital anomaly/birth defect.

Important medical events that may not result in death, be life-threatening, or require hospitalization may be considered an SAE when, based on appropriate medical judgment, they may jeopardize the patient or the patient may require medical or surgical intervention to prevent one of the outcomes listed in the above definitions.

### Confidentiality Statement

---

Data and information contained in this document are considered to constitute trade secrets and confidential commercial information, and the legal protections provided to such trade secrets and confidential information are hereby claimed under the applicable provisions of applicable law. No part of this document may be publicly disclosed without the written consent of Philip Morris Products S.A.

---

Any pre-planned hospitalizations that are known at the time of signing the study participation ICF will not be recorded as SAEs (they will be recorded only as AEs). However, any AE that occurs during this pre-planned hospitalization will be considered according to the above definitions.

## 8.2 Assessment of Adverse Events

The Investigator is responsible for obtaining, assessing and documenting all AEs during the study.

### 8.2.1 Assessment of Adverse Events

Adverse event information will be collected from the time of signature of the study participation ICF onwards until the end of the safety follow-up period either by the Investigator via spontaneous reporting or by the use of consistent, open, non-directive questions from study site collaborators (*e.g.*, “Have you had any health problems since the previous visit/How have you been feeling since you were last asked?”). The main source for AE collection will be face-to-face interview(s) with the patient.

Information recorded will include: verbatim description of the AE, start and stop dates and times, seriousness, severity (intensity), action taken (*e.g.*, whether or not the AE led to the patient’s withdrawal from the study), and outcome (*e.g.*, resolved, withdrawal due to AE).

For each AE, the intensity (severity) will be graded on a 3-point intensity scale (mild, moderate, severe) using the definitions provided in section 8.2.3.

Any exacerbation/worsening of an AE or pre-existing condition shall be evaluated and recorded.

Correct medical terminology/concepts are preferred when recording AE terms, and abbreviations must be avoided. Wherever possible, a diagnosis is to be used to describe an AE rather than individual signs and symptoms (*e.g.*, record ‘pneumonia’ rather than ‘fever,’ ‘cough,’ ‘pulmonary infiltrate,’ or ‘septicemia,’ rather than ‘fever’ and ‘hypotension’ following blood sample).

Any AE that meets the serious criteria must be recorded both on the AE report form of the CRF and on a separate SAE report form (section 8.3).

### 8.2.2 Period of Collection

Any AEs (including SAEs) will be captured by the study site collaborators and assessed by the Investigator(s) or designee(s) in order to establish relationship to Investigational Products and study procedures. AEs will be collected from the time the patients have signed their ICFs until the end of the safety follow-up period.

#### Confidentiality Statement

---

Data and information contained in this document are considered to constitute trade secrets and confidential commercial information, and the legal protections provided to such trade secrets and confidential information are hereby claimed under the applicable provisions of applicable law. No part of this document may be publicly disclosed without the written consent of Philip Morris Products S.A.

---

All collected AEs will be reported in the clinical study report (CSR) and in accordance with the respective local regulatory guidelines.

#### 8.2.2.1 Screening Visit (V1)

All existing health conditions identified during the screening visit and judged by the Investigator as preexisting condition will be recorded as concomitant disease and the patient's eligibility for admission to the study will be reviewed.

#### 8.2.2.2 From End of V1 until the End of Study

From V1 onwards until the EOS, all AEs will be documented.

Any new, clinically relevant, abnormal finding or worsening of a pre-existing condition/concomitant disease detected during the study will be documented as an AE and/or SAE and assessed by the Investigator or designee. During the safety follow-up period AEs and/or SAEs will be recorded only if reported spontaneously by the patient.

SAEs will be reported by the Investigator as described in this document and the safety management plan (SMP).

At the end of the safety follow-up period, all ongoing non-serious AEs will be documented as "ongoing" and no follow-up information will be sought for on them anymore by the Investigator or designee. At that point, the Investigator will assess whether the patient should be referred to his/her General Practitioner to have their ongoing AEs addressed accordingly.

All SAEs will be actively followed up by the Investigator, despite their continuation after the end of the safety follow-up period, until their resolution, stabilization (*i.e.*, no worsening of the condition), or until an acceptable explanation has been found (*e.g.*, a chronic condition).

#### 8.2.3 Intensity of Adverse Event

For each AE, the intensity will be graded by the Investigator on a 3-point intensity scale (mild, moderate, severe) using the following definitions:

**Mild:** The AE is easily tolerated and does not interfere with daily activity.

**Moderate:** The AE interferes with daily activity, but the patient is still able to function.

**Severe:** The AE is incapacitating and requires medical intervention.

#### 8.2.4 Relationship to Investigational Product and Relationship to Study Procedures

In general, all AEs and/or SAEs will be assessed by the Investigator as either 'related' or 'not related' to IP (*i.e.*, IQOS or cigarette) as described below. In addition to the assessment of the

#### Confidentiality Statement

---

Data and information contained in this document are considered to constitute trade secrets and confidential commercial information, and the legal protections provided to such trade secrets and confidential information are hereby claimed under the applicable provisions of applicable law. No part of this document may be publicly disclosed without the written consent of Philip Morris Products S.A.

---

relationship of the clinical event to the IP, the Investigator shall document a potential relationship of the clinical event to any particular study procedure.

**Not related:** The temporal relationship of the dental or clinical event to IP administration or to a study procedure makes a causal relationship unlikely, or, concomitant medication, therapeutic interventions, or underlying conditions provide a sufficient explanation for the observed event.

**Related:** The temporal relationship of the dental or clinical event to study IP administration or to a certain study procedure makes a causal relationship possible, and concomitant medication, therapeutic interventions, or underlying conditions do not provide a sufficient explanation for the observed event.

### 8.2.5 Expectedness

Any AE assessed as related to the IP will be assessed for its expectedness. An AE will be regarded as ‘unexpected’ if its nature or severity is not consistent with information already known about the IP, and is not listed in the current SPI [81].

### 8.2.6 Medical Monitor

All Investigator of this study are dentists. A medical monitor will be designated by Sponsor or authorized representative to answer any medical question that a dentist may have on any medical condition besides dental conditions, as well as on any question related to the safety of the patient (*i.e.*, AE/SAE).

## 8.3 Reporting and Follow-Up of Serious Adverse Events

Any SAEs reported or observed during the study whether or not attributable to the IP, or to any study procedures, or any SAE related to the product and spontaneously reported after the safety follow-up period must be reported by the Investigator **within 24 hours after first awareness by any party involved in the study** to [REDACTED] and to the Sponsor.

An SAE report form must be e-mailed or faxed as an attachment to:

[REDACTED] :	Phone number:	[REDACTED]
	E-mail:	[REDACTED]
	Fax:	[REDACTED]
	Address:	[REDACTED] [REDACTED] [REDACTED] [REDACTED]

### Confidentiality Statement

Data and information contained in this document are considered to constitute trade secrets and confidential commercial information, and the legal protections provided to such trade secrets and confidential information are hereby claimed under the applicable provisions of applicable law. No part of this document may be publicly disclosed without the written consent of Philip Morris Products S.A.

**Sponsor:** [REDACTED]      **Phone number:** [REDACTED]

**E-mail:** [REDACTED]

**Address:** Philip Morris Products S.A.  
R&D Innovation Cube  
[name]  
[name]  
Switzerland

The Investigator/head of the investigational site is responsible for local reporting (*i.e.*, to the IRB) of SAEs that occur during the study, according to local regulations.

Any additional/follow-up information that becomes available after the initial SAE report form has been completed will be forwarded to [REDACTED] and the Sponsor **within 24 hours after first awareness** by any person at the site using a new SAE report form and indicating that this is a follow-up report.

The follow-up SAE report form must include the minimum information required for form completion and only changed/new information needs to be specified. Information provided in the follow-up SAE report form supersedes any information that was initially reported.

All SAEs will be actively followed up by the Investigator until their resolution or until the Investigator considers the event to be stabilized (*i.e.*, no worsening of condition), or until an acceptable explanation has been found (*e.g.*, a chronic condition). The details of the SAE management will be provided in a separate document, namely the safety management plan (SMP) for this study.

The SAE report form to be used in this study is provided as a separate document. All SAEs will be recorded on the relevant CRF page, in addition to the SAE report form.

#### **8.4 Reporting of other events critical to safety evaluations**

An ongoing medical condition, clinically relevant finding detected during the screening visit (V1), will be considered a concomitant disease and the patient's eligibility for participating to the study will be reviewed.

Any new, clinically relevant, abnormal finding or worsening of a pre-existing condition detected during the study after the screening visit until the end of the study will be documented as an AE.

Any new onset of symptoms or worsening of pre-existing symptoms identified through the study questionnaires may be documented as AEs at the discretion of the Investigator.

#### **Confidentiality Statement**

---

Data and information contained in this document are considered to constitute trade secrets and confidential commercial information, and the legal protections provided to such trade secrets and confidential information are hereby claimed under the applicable provisions of applicable law. No part of this document may be publicly disclosed without the written consent of Philip Morris Products S.A.

---

In order to avoid duplicate reports, the patients will be instructed to report AEs, SAEs and occurrences of malfunction of the IQOS device only to a member of the study staff and not to the IQOS hotline.

## 8.5 Reporting and Follow-Up of Pregnancies

For pregnancies detected between the time of signature of the study participation ICF and the enrollment of the patient, the patient will be considered as a screen failure. In that situation, the pregnancy will not be reported to the Sponsor, however, the identified pregnancy(ies) must be captured in the screen failure CRF. No pregnancy form will be filled.

For pregnancies detected between enrollment and V2 prior to randomization, patients will be discontinued, and reported as “enrolled but not randomized” patients. Early termination procedures shall apply. No pregnancy form will be filled.

Any pregnancy detected after randomization, must be reported by the Investigator to the Sponsor within 24 hours of the first awareness and must be followed-up up to 8 weeks after the pregnancy outcome is reached. This also includes pregnancies spontaneously reported to the Investigator after the end of the study for a patient.

The Investigator will complete a pregnancy form (provided as a separate document) for all pregnancies diagnosed (including positive urine pregnancy tests) after randomization.

The procedure to report a pregnancy and provide any additional/follow-up information to [REDACTED] and the Sponsor must be followed in the same manner and within the same timelines as described for an SAE (section 8.3). No invasive procedures must be done in such patients after the discovery of pregnancy. [REDACTED] will follow up pregnancies only if they were detected after first product use (*i.e.*, IQOS or cigarettes after V2). If pregnancies are to be followed-up, they will be followed-up until an outcome is reached (*e.g.*, normal delivery, spontaneous abortion, or voluntary termination) and also until 8 weeks after delivery.

Any pregnancy complication, adverse pregnancy outcome, or maternal complications will be recorded as an AE (or SAE).

The Principal Investigator/head of the investigational site is responsible for informing the IRB of any pregnancy that occurs during the study and its outcome, according to local regulations.

## 8.6 Adverse Events Leading to Discontinuation

Patients who are discontinued from the study because of an AE will undergo the early termination procedures, as described in section 9.6, as soon as possible and will enter the safety follow-up period. The Investigator will follow up these AEs as described in section 8.2.2.

## 8.7 Device Events / Investigational Product Malfunction and Misuse

Any occurrences of device events, including IQOS malfunction (*e.g.*, holder does not charge when inserted into the charger) or misuse (use not in accordance with its label and instruction) by a patient, will be documented by a site collaborator in a device issue log developed by the site.

Investigational product misuse may result in use-related hazards (section 2.3.4).

Furthermore, any misuse or malfunction of the IQOS that leads to an AE/SAE will follow the same processes as described above for the reporting of the AE/SAE.

## 9 STUDY ACTIVITIES

A detailed schedule of assessment can be found in Appendix 1.

If no start time for the procedures is provided, then the procedure can be performed at any time during the visit. Assessments will be conducted only by qualified and trained site personnel. Toothbrush instructions will be provided throughout the study as per standard of care.

From V2 to V4, patients will be asked not to drink, eat, chew gum, use mouth rinse or brush their teeth for at least 30 minutes before collection of oral samples (*i.e.*, SP, GCF or buccal swabs).

### 9.1 Screening, Enrollment and Baseline Visit: V1

The screening, enrollment and baseline visit (V1) will be scheduled within 2 weeks (Day -14 to -7) prior to randomization visit (V2).

Patient will sign the study participation ICF before the start of any procedure, and will enter Screening. All eligibility criteria will be checked, including periodontal assessment, which will be also used as baseline assessment for enrolled patients.

Table 3 shows the assessments that will be performed at the screening, enrollment and baseline visit:

**Table 3 Schedule - Screening, Enrollment and Baseline Visit: V1**

Time	Sample collection	Procedures	Additional information
Start of procedure		Screening, Enrollment and Baseline	
Start of the visit 		ICF signature	
During the visit		Advice on the risks of smoking/smoking cessation advice and debriefing on IQOS	
Before enrollment		Demographics data	Sex, date of birth, ethnicity
		Dental/medical history, including history of alcohol or drug abuse, concomitant diseases, Prior medication and/or concomitant medication / Procedures	
	U	Spot urine collection for pregnancy (all females) and cotinine tests, and collection	Pregnancy test (all females): at the study site

 The informed consent process can be started as soon as the patient is invited to participate in the study, but the ICF must be signed no later than before the first assessment at V1.

#### Confidentiality Statement

Data and information contained in this document are considered to constitute trade secrets and confidential commercial information, and the legal protections provided to such trade secrets and confidential information are hereby claimed under the applicable provisions of applicable law. No part of this document may be publicly disclosed without the written consent of Philip Morris Products S.A.

Time	Sample collection	Procedures	Additional information
Start of procedure	Screening, Enrollment and Baseline		
		for NEQ, total NNAL, CEMA and creatinine samples.	Cotinine test: at the study site. Cotinine $\geq$ 200 ng/mL Process samples for NEQ, total NNAL, CEMA, creatinine analysis according to laboratory manual/SHM.
		IQOS presentation	To all males. For females, only those who presented negative pregnancy test.
		Smoking history	Patients will be questioned on their smoking history.
		Tobacco or nicotine containing product use self-reporting	Patients will answer this questionnaire on site, with instructions from study staff so that they can then fill it alone on a monthly basis  . Distribution of the diaries for the next Visit.
		Readiness to comply to study procedures, and to use the product he/she has been allocated to for the duration of the study	
		Patient is not planning to quit smoking during the study	
		Periodontal assessment:	Last assessment performed as part of the eligibility criteria, to avoid unnecessary examination for those patients who are in any case not eligible.
		Full mouth PD	
		Full mouth CAL	
		Full mouth BOP	
		Full mouth tooth mobility	
		Full mouth PCR 	
		Judgment on eligibility	All eligibility criteria must be checked.

 For the questionnaire, “monthly” can be considered as 30 days, or as a calendar month. A flexibility of  $\pm$  2 day is allowed to fill it.

 PCR can be performed after enrollment based on PI’s decision.

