### Confidentiality Statement

---

Data and information contained in this document are considered to constitute trade secrets and confidential commercial information, and the legal protections provided to such trade secrets and confidential information are hereby claimed under the applicable provisions of applicable law. No part of this document may be publicly disclosed without the written consent of Philip Morris Products S.A.

---

---

Periodontal assessment	Full mouth assessment of PD, CAL, BOP, tooth mobility, PCR, and assessment of gingival inflammation of the target teeth.
Randomization	After all assessments of V1 have been completed, patients will be randomized to IQOS or cigarette arm. Patients will be informed of their randomized study arm by the study site during V2. All patients will be instructed to continue to solely use their assigned product until they complete the study.
Safety follow-up	After the day of Discharge at V4, patients will enter into a 7-day safety follow-up for the recording of spontaneously reported new AEs/SAEs and the follow-up of ongoing AEs/SAEs by the study site.
Screen failure	Patient who signs ICF but was not enrolled. Re-screening of patients who did not meet any entry criteria will not be permitted.
Target site	The site of a target tooth, preferably the deepest of the tooth, from which the GCF will be collected.
Target tooth	At V1, for all eligible patients, the Investigator or designee will designate 4 target teeth, i.e. , preferably one per quadrant. Teeth with PD $\geq$ 5 mm but < 7 mm will be preferably selected. If their location does not correspond to one per quadrant, the Investigator or designee will designate the target teeth preferably as single-rooted, and distributed as evenly as possible. Target teeth identification will be reported in the CRF.

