#### 7.3.5.8 Plaque Control Record (PCR)

Presence of the plaque on individual tooth surfaces in full mouth is assessed and PCR (%) is calculated.

According to the PCR of O'Leary et al. [20], plaque retention in the dentogingival areas of mesial, distal, facial and lingual tooth surfaces is determined to be YES or NO and recorded at V1, V3 and V4.

Usual plaque disclosing agent is used in each site and the product name of the plaque disclosing agent will be recorded.

For each subject, PCR (%) is calculated by the following formula:

$$Full\ Mouth\ PCR\ (\%) = 100 * \frac{1}{t} \sum_{i=1}^t \sum_{j=1}^{s_i} \frac{PCR_{ij}}{s_i}$$

Where  $PCR_{ij}$  is a binary response (Yes = 1, No = 0) of PCR at tooth  $i$ ,  $i = 1, \dots, t$  at the surface  $j$  where  $j = 1, \dots, s_i$ .

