#### 7.5.4 Assessments in Subgingival Plaque

SP will be collected from 4 target teeth, at V1 and V4 in order to evaluate the microbiological status. The sampling should be performed before periodontal assessments, except at V1, when it will be performed after periodontal assessments and designation of target teeth. If plaque sample is too small, additional collection can be performed on mesiobuccal SP of second molars, which needs to be recorded by the examiner. These teeth are the same than those selected for GCF collection (section 7.5.3). DNA isolation from these samples will enable the evaluation of the bacterial diversity and the detection of the abundance of bacteria in these samples. Some human host DNA (*i.e.*, of the patient) will also be isolated, however, the host DNA sequences obtained during the DNA sequencing will be filtered out of the raw sequencing data before analysis, and no formal analysis of the patient DNA will be performed.

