#### Confidentiality Statement

Data and information contained in this document are considered to constitute trade secrets and confidential commercial information, and the legal protections provided to such trade secrets and confidential information are hereby claimed under the applicable provisions of applicable law. No part of this document may be publicly disclosed without the written consent of Philip Morris Products S.A.

Time	Sample collection	Procedures	Additional information
Start of procedure	Screening, Enrollment and Baseline		
		Enrollment	If all eligibility criteria are met.
		Designation of 4 target teeth and 4 target sites	Target teeth: preferably 4 teeth with $\geq 5$ mm initial PD, from which SP and GCF will be collected at their respective visits indicated in the Appendix 1. Target sites: preferably the deepest sites of the target teeth.
After enrollment		Gingival inflammation of target teeth	Part of periodontal assessment, to be performed after designation of 4 target teeth
	SP	Collect from 4 target teeth	For microbiological status. Store the sample according to laboratory manual/SHM.
		Supragingival scaling	
		AE/SAE recording	
For screen failures		Discard any urine samples that might have been collected for patients who are not enrolled.	
End of the visit			

Abbreviations: AE = Adverse event; BOP = Bleeding on probing; CAL = Clinical attachment level; CEMA = 2-cyanoethylmercapturic acid; GCF = Gingival crevicular fluid; NEQ = nicotine equivalents, consisting of the molar sum of free nicotine, nicotine-glucuronide, free cotinine, cotinine-glucuronide, free trans-3'-hydroxycotinine and trans-3'-hydroxycotinineglucuronide; NNAL = 4-[methylnitrosamino]-1-[3-pyridyl]-1-butanol; PCR = Plaque control record; PD = Pocket depth; SAE = Serious adverse event; SHM = Sample handling manual; SP = Subgingival plaque; U = Urine

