**Table 5 Time Schedule – 3 Months Visit: V3**

Time	Sample collection	Procedures	Additional information
Start of procedure			
Start of the visit		Advice on the risks of smoking/smoking cessation advice and debriefing on IQOS.	
During the visit		Tobacco or nicotine containing product use self-reporting	Collection of the diaries from the previous Visit, and distribution of the diaries for the next Visit
		Concomitant medication / Procedures	
	U	Spot urine collection for pregnancy (all females), and collection for NEQ, total NNAL, CEMA and creatinine samples.	Test at the study site. Store the sample according to SHM
	BS	Derived from the right and left cheek	Store the sample according to SHM for transcriptomics evaluation.
	GCF	Collect from 4 target sites	Same teeth as SP collection at V1. Store the sample according to SHM
		Periodontal assessment	Same examiner as V1
		Full mouth PD	Examiner wears mask.
		Full mouth CAL	Patients wash hands.
		Full mouth BOP	
		Full mouth tooth mobility	
		Gingival inflammation of the target teeth	
		Full mouth PCR	
		Maintenance treatment	

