**Confidentiality Statement**

Data and information contained in this document are considered to constitute trade secrets and confidential commercial information, and the legal protections provided to such trade secrets and confidential information are hereby claimed under the applicable provisions of applicable law. No part of this document may be publicly disclosed without the written consent of Philip Morris Products S.A.

		Reason to change : not all sites have the same practices, thus added clarification.
9.3	Table 5	Amended text (added next to Tobacco or nicotine containing product use self-reporting) : Collection of the diaries from the previous Visit, and distribution of the diaries for the next Visit. Reason to change : to clarify when questionnaires are distributed and collected.
9.3	Table 5	Old text : Concomitant medication Amended text : Concomitant medication / procedures Reason to change : “procedures” was added to distinguish from concomitant medication
9.3	Table 5	Moved text (After “gingival inflammation”) : Full mouth PCR Reason to change : a PI commented that PCR can prevent proper evaluation of gingival inflammation.
9.4	Table 6	Amended text (added next to Tobacco or nicotine containing product use self-reporting) : Collection of the diaries from the previous Visit, including questionnaire of Month 6. Reason to change : to clarify when questionnaires are collected.
9.4	Table 6	Old text : Concomitant medication Amended text : Concomitant medication / procedures Reason to change : “procedures” was added to distinguish from concomitant medication
9.4	Table 6	Moved text (After “gingival inflammation”) : Full mouth PCR Reason to change : a PI commented that PCR can prevent proper evaluation of gingival inflammation.
11.2.2	Coding	Old text : WHO Drug Dictionary Enhanced and Anatomical Therapeutic and Chemical Classification System

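### At V1 the default order puts the plaque-disclosing dye before the gingival index rating, while V3 and V4 list it after, so the baseline for change in GI may not match follow-up

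*Protocol*

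**What the plan says.** Protocol Section 7.3.5.8 makes PCR a dye-based procedure, with the product left to the site: "Usual plaque disclosing agent is used in each site and the product name of the plaque disclosing agent will be recorded".

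Section 9.1, Table 3 (V1) lists full-mouth PCR with PD, CAL, BOP and mobility under the before-enrollment timing. Footnote 2 adds that "PCR can be performed after enrollment based on" the PI's decision. GI comes under the after-enrollment timing and is described as "Part of periodontal assessment, to be performed after designation of 4 target teeth". SP collection and supragingival scaling follow it.

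Table 5 (V3) and Table 6 (V4) list the row "Gingival inflammation of the target teeth" ahead of full-mouth PCR. Appendix 5 explains the move with the remark that "a PI commented that PCR can prevent proper evaluation of gingival inflammation". It gives the same reason for adding footnote 2 at V1.

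Change in GI score at 3 and 6 months is a secondary endpoint (protocol Section 3.2). Protocol Section 12.7 and SAP Section 9.5.2.1 treat it descriptively, and the SAP adds shift tables on the individual GI values.

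**The concern.** The sponsor took seriously the possibility that dye spoils the GI rating, and reordered the follow-up visits accordingly. At baseline it added only an option. A site that follows Table 3 as printed rates baseline GI on dyed teeth and gums, then rates follow-up GI before any dye.

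The GI criteria in Section 7.3.5.7 rest partly on colour, so the two ratings may not be like-for-like. Change in GI subtracts one from the other, and the shift tables would show single-grade misratings directly. Because both the order and the agent can differ by site, any artefact may differ by site as well.

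**Working it through.** No arithmetic applies; the check is a comparison of the order of procedures.

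| Visit | Timing label in the table | Listed order | What fixes the order |
|---|---|---|---|
| V1 (Table 3) | Before enrollment, then after enrollment | PD, CAL, BOP, mobility, PCR; enrollment; target teeth; GI; SP; scaling | The timing labels put PCR before GI; footnote 2 is optional |
| V3 (Table 5) | During the visit | PD, CAL, BOP, mobility; GI; PCR | Row order plus the reason in Appendix 5 |
| V4 (Table 6) | During the visit | SP; PD, CAL, BOP, mobility; GI; PCR | SP first by rule in Section 7.5.4; GI before PCR by row order plus the reason in Appendix 5 |

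1. *Does footnote 2 settle V1?* No. GI, SP and scaling all fall after enrollment, so a deferred PCR may still come before GI. Nor does the footnote keep PCR ahead of scaling, so it does not protect PCR's own baseline.

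2. *Does the flexibility in Section 9 settle it?* No. That section frees the order only where no start time is given. Table 3 separates before from after enrollment; Tables 5 and 6 do not assign separate times to PCR and GI. V1 is the only visit where the stated timing puts dye first.

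3. *Is PCR needed before enrollment?* No inclusion or exclusion criterion in Section 5.1 uses it. GI and SP need the target teeth, which are designated before both. PCR can therefore follow them and still precede scaling.

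4. *Is the SP text consistent?* No. Section 7.5 says SP is sampled before the periodontal assessment and states no exception. Section 7.5.4 applies the same rule "except at V1, when it will be performed after periodontal assessments and designation of target teeth". The protocol defines periodontal assessment as "Full mouth assessment of PD, CAL, BOP, tooth mobility, PCR, and assessment of gingival inflammation of the target teeth", so read literally Section 7.5.4 also places V1 SP sampling after PCR.

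5. *Which analyses are exposed?* Those that use GI: the descriptive summaries, shift tables and plots in SAP Section 9.5.2.1. GI is not a covariate in the primary PD model, the CAL model or the biomarker models.

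**The case against.** The sponsor did act at V1. Footnote 2 was added for this very reason, and a PI who sees a problem can already rate GI before dye. This stands: a baseline under dye is a possibility set by the default, not an established fact for any given share of patients.

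The follow-up order is also not a hard rule. Under Section 9 a site could apply dye before GI at V3 or V4. This stands too; the contrast between visits rests on row order and stated intent.

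Colour is only part of the GI scale. Edema, glazing, ulceration and bleeding also count, and bleeding on probing helps separate grade 1 from grade 2. Dye could therefore leave many ratings unchanged, and errors could go either way. The documents give no basis for a figure.

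A reader might infer that dye also distorts the V1-to-V4 microbiome comparison. The documents do not support that. The reason in Appendix 5 concerns gingival inflammation only, and nothing links a disclosing agent to the sequencing of subgingival plaque. V1 SP also follows probing, by the open exception in Section 7.5.4, so the V1 and V4 samples would differ in that respect whatever the position of PCR.

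**Conclusion.** The point holds in a limited form. The V1 default permits, and as printed directs, a GI baseline rated after dye, while follow-up is listed as rated before it. This affects the reading of within-group change in GI and the GI shift tables, and may add site-to-site variation.

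Its size is unknown. It depends on how many PIs used footnote 2 to rate GI first, and on how far each site's agent alters the rating; the documents give neither.

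A reader might also infer bias between the arms. That is not expected for the randomized comparison, because V1 assessments are completed before randomization under both arms alike. The SAP does summarise GI by actual product use, a grouping that randomization does not protect, and plans no site adjustment for it. Uneven order across sites could therefore blur that comparison, but nothing in the documents suggests a direction. No planned hypothesis test uses GI.

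**What to change.** In Table 3, move full-mouth PCR to after the GI rating and, for consistency with V4, after SP collection, and before supragingival scaling, for all patients. Replace footnote 2 with that order. Reconcile Section 7.5 with Section 7.5.4 on SP timing at V1, and reword Section 7.5.4 so that it no longer places V1 SP after PCR. Align Appendix 1 footnote h, which counts PCR and GI within the full examination described as the last eligibility step.

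If V1 data already exist, document the PCR and GI order by site where source records allow, and repeat the GI summary in patients rated before dye. The protocol sections on these assessments do not ask for that order to be recorded, so it may not be recoverable. In that case, state the limitation wherever change in GI is reported.

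The cost is a minor written amendment, which under Section 1.1 needs approval by the sponsor and the Principal Investigators and submission to the IRB, plus notice to sites. No procedure is added, and screen failures are spared the dye.
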